7.1.3.2 Future Biomedical Research

The following specimens are to be obtained as part of Future Biomedical Research:

- Buccal swabs for genomics use
- Leftover serum samples collected in the main study, which would routinely be discarded after the main study is over

7.1.4 Other Procedures

7.1.4.1 Withdrawal/Discontinuation

Subjects who discontinue/withdraw from vaccination prior to completion of the vaccination regimen should be encouraged to continue to be followed for all remaining study visits.

When a subject discontinues/withdraws from participation in the trial, all applicable activities scheduled for the final trial visit should be performed at the time of discontinuation. Any adverse events which are present at the time of discontinuation/withdrawal should be followed in accordance with the safety requirements outlined in Section 7.2 - Assessing and Recording Adverse Events.

7.1.4.1.1 Withdrawal From Future Biomedical Research

Subjects may withdraw their consent for Future Biomedical Research and have their specimens and all derivatives destroyed. Subjects may withdraw consent at any time by contacting the principal investigator for the main trial. If medical records for the main trial are still available, the investigator will contact the Sponsor using the designated mailbox [REDACTED] and a form will be provided by the Sponsor to obtain appropriate information to complete specimen withdrawal. Subsequently, the subject's specimens will be removed from the biorepository and be destroyed. A letter will be sent from the Sponsor to the investigator confirming the destruction. It is the

responsibility of the investigator to inform the subject of completion of destruction. Any analyses in progress at the time of request for destruction or already performed prior to the request being received by the Sponsor will continue to be used as part of the overall research trial data and results. No new analyses would be generated after the request is received.

In the event that the medical records for the main trial are no longer available (e.g., if the investigator is no longer required by regulatory authorities to retain the main trial records) or the specimens have been completely anonymized, there will no longer be a link between the subject's personal information and their specimens. In this situation, the request for specimen destruction cannot be processed.

7.1.4.2 Blinding/Unblinding

When the investigator or sub-investigator needs to identify the drug used by a subject and the dosage administered in case of emergency e.g., the occurrence of serious adverse experiences, he/she will contact the emergency unblinding call center by telephone and make a request for emergency unblinding. As requested by the investigator or sub-investigator the emergency unblinding call center will provide the information to him/her promptly and report unblinding to the sponsor. The emergency unblinding call center will make a record promptly however, the investigator or sub-investigator must enter the intensity/toxicity grade of the adverse experiences observed, their relation to study drug, the reason thereof, etc., in the medical chart etc., before unblinding is performed.

Additionally, the investigator must go into the IVRS system and perform the unblind in the IVRS system to update drug disposition. In the event that the emergency unblinding call center is not available for a given site in this trial, IVRS/IWRS should be used for emergency unblinding in the event that this is required for subject safety.

In the event that unblinding has occurred, the circumstances around the unblinding (e.g., date and reason) must be documented promptly, and the Sponsor Clinical Director notified as soon as possible. Only the principal investigator or delegate and the respective subject's code should be unblinded. Trial site personnel and Sponsor personnel directly associated with the conduct of the trial should not be unblinded.

At the end of the trial, random code/disclosure envelopes or lists and unblinding logs are to be returned to the Sponsor or designee.

7.1.4.3 Domiciling

Adult subjects will report to the clinical research unit (CRU) on the day of trial vaccination administration (Day 1) and remain in the CRU for 30 minutes following vaccination. Subjects will return 30 days later for Visit 2.

Infant subjects will report to the CRU on the day of the administration of study vaccine (Visit 1, 2, 3, and 5) and remain in the unit for 30 minutes postvaccination. At the discretion of the investigator, subjects may be requested to remain in the CRU longer. Infants will return to the CRU at Visits 4 and 6 for blood draws.

7.1.4.4 Calibration of Critical Equipment

The investigator or qualified designee has the responsibility to ensure that any critical device or instrument used for a clinical evaluation/test during a clinical trial that provides important information about inclusion/exclusion criteria and/or safety or efficacy parameters shall be suitably calibrated and maintained to ensure that the data obtained is reliable and/or reproducible. Documentation of equipment calibration must be retained as source documentation at the trial site.

Critical Equipment for this trial includes:

- Refrigerators
- -20° freezers
- Centrifuges

7.1.5 Visit Requirements

Visit requirements are outlined in Section 6.0 - Trial Flow Chart. Specific procedure-related details are provided above in Section 7.1 - Trial Procedures.

7.1.5.1 Screening

Screening procedures will be performed at Visit 1. A separate screening visit is not required.

7.1.5.2 Treatment Period/Vaccination Visit

Adult subjects will be required to come to the clinic for 2 visits. Infant subjects will be required to come to the clinic for 6 visits. See Section 6.0 for details.

7.1.5.3 Post-Trial

This protocol does not require post trial visits.

7.2 Assessing and Recording Adverse Events

An adverse event is defined as any untoward medical occurrence in a patient or clinical investigation subject administered a pharmaceutical product and which does not necessarily have to have a causal relationship with this treatment. An adverse event can therefore be any unfavourable and unintended sign (including an abnormal laboratory finding, for example), symptom, or disease temporally associated with the use of a medicinal product or protocol-specified procedure, whether or not considered related to the medicinal product or protocol-specified procedure. Any worsening (i.e., any clinically significant adverse change in frequency and/or intensity) of a preexisting condition that is temporally associated with the use of the Sponsor's product, is also an adverse event.

Changes resulting from normal growth and development that do not vary significantly in frequency or severity from expected levels are not to be considered adverse events. Examples of this may include, but are not limited to, teething, typical crying in infants and children and onset of menses or menopause occurring at a physiologically appropriate time.

Sponsor's product includes any pharmaceutical product, biological product, device, diagnostic agent or protocol-specified procedure, whether investigational (including placebo or active comparator medication) or marketed, manufactured by, licensed by, provided by or distributed by the Sponsor for human use.

Adverse events may occur during clinical trials, or as prescribed in clinical practice, from overdose (whether accidental or intentional), from abuse and from withdrawal.

All adverse events that occur after the consent form is signed but before allocation/randomization must be reported by the investigator if they cause the subject to be excluded from the trial, or are the result of a protocol-specified intervention, including but not limited to washout or discontinuation of usual therapy, diet, placebo treatment or a procedure. From the time of allocation/randomization through 14 days (42 days for live attenuated vaccines) following the first vaccination(s) and from the time of any subsequent vaccination(s) through 14 days (42 days for live attenuated vaccines) thereafter, all adverse events must be reported by the investigator. Such events will be recorded at each examination on the Adverse Event case report forms/worksheets. The reporting timeframe for adverse events meeting any serious criteria is described in section 7.2.3.1. The investigator will make every attempt to follow all subjects with non-serious adverse events for outcome.

Electronic reporting procedures can be found in the EDC data entry guidelines. Paper reporting procedures can be found in the Investigator Trial File Binder (or equivalent).

7.2.1 Definition of an Overdose for This Protocol and Reporting of Overdose to the Sponsor

In this trial, an overdose is the administration of more than 1 dose of any individual study vaccine in any 24-hour period.

If an adverse event(s) is associated with (“results from”) the overdose of Sponsor's product or vaccine, the adverse event(s) is reported as a serious adverse event, even if no other seriousness criteria are met.

If a dose of Sponsor's product or vaccine meeting the protocol definition of overdose is taken without any associated clinical symptoms or abnormal laboratory results, the overdose is reported as a non-serious Event of Clinical Interest (ECI), using the terminology “accidental or intentional overdose without adverse effect.”

All reports of overdose with and without an adverse event must be reported by the investigator within 24 hours to the Sponsor either by electronic media or paper. Electronic

reporting procedures can be found in the EDC data entry guidelines. Paper reporting procedures can be found in the Investigator Trial File Binder (or equivalent).

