5.6 Rescue Medications & Supportive Care

Infant subjects who fail to achieve adequate serologic responses following the third dose of study vaccine will be offered an additional dose of licensed pneumococcal conjugate vaccine outside of this protocol. Any study subject with serotype-specific pneumococcal IgG (as measured by Pn ECL assay) below 0.35 μ g/mL for serotype 19A (individually) and/or 4 or more serotypes in common between V114 and Prevnar 13TM at 1 month PD3, will be given one dose of licensed pneumococcal conjugate vaccine as soon as possible after serological results are available. All subjects who meet the rescue criterion must be discontinued from the study prior to administering the additional dose of licensed pneumococcal conjugate vaccine. The discontinuation date should be the date the parent/legal guardian was notified of the child's meeting the rescue criterion. Adverse events or changes to medical history occurring after the 14 days of safety follow up for Dose 3 and the discontinuation should be reported in the database; no additional immunogenicity blood sample should be drawn. If an SAE occurs between the 14 days of safety follow up for Dose 3 and the discontinuation, that event must be reported. The serologic threshold value of 0.35 μ g/mL was recommended by a WHO expert panel as an acceptable threshold value for evaluating the clinical performance of pneumococcal conjugate vaccines in infants [3],[4]. Adequate treatment provisions,

including epinephrine, should be available for immediate use should an anaphylactic or anaphylactoid reaction occur.

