5.11 Clinical Criteria for Early Trial Termination

Early trial termination will be the result of the criteria specified below:

The eDMC will be provided with the following stopping rules as guidance for temporarily halting or terminating the study:

If any of the following events occurs, administration of study vaccine will be temporarily discontinued until a thorough review of accumulated safety data is undertaken by the eDMC, the investigator, and /or the SPONSOR's representative.

- Death in any subject, unless the cause of death is due to obvious alternative etiology;
- Unexpected life-threatening event in any subject, unless due to obvious alternative etiology. Event should not have been previously observed with similar pneumococcal vaccines, or vaccines administered concomitantly in this study;
- Any serious adverse event, unless due to obvious etiology, with the exception of those already reported for pneumococcal conjugate vaccines or for other concomitantly administered vaccines and deemed related to those vaccines;
- Event which in the opinion of the investigator and/or safety monitoring committee contraindicates further dosing of additional subjects.

Conclusions about the overall safety of the investigational product will otherwise be determined from any SAE and solicited systemic AEs with a severe intensity rating, regardless of relationship to vaccination. The relationship to study vaccine is determined by the study investigator.

The study site and SPONSOR's personnel involved in the conduct of the study (excluding the MRL statistician and statistical programmer) will remain blinded as to the treatment allocation of the study subject.

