Visit Timing:	Age:~2 months DOSE 1	Age:~4 months DOSE 2	Age:~6 months DOSE 3	30 days after Visit 3	Age:~12 to 15 months DOSE 4	30 days after Visit 5
Visit Window:	≥42 days of age to ≤90 days of age	4 months of age to 1 day prior to 5 months of age	6 months of age to 1 day prior to 7 months of age	28 to 42 days PD3	12 months of age to 1 day prior to 16 months of age	28 to 42 days PD4
Administrative Procedures						
Informed Consent ^b	X					
Informed Consent for Future Biomedical Research (FBR) ^c	X					
Inclusion/Exclusion Criteria	X					
Subject Identification Card	X					
Medical History	X					
Update Medical History (New condition not already recorded as medical history or adverse experiences)		X	X	X	X	X
Concomitant Medication Review	X	X	X	X	X	X
Vaccination Allocation/Randomization	X					
Study Vaccine Administration ^d	X	X	X		X	
Childhood Vaccines ^e	X	X	X		X	
Provide Electronic Vaccination Report Card (VRC)	X					
Review VRC data ^f		X	X	X		X
Clinical Procedures/Assessments						
Full Physical Examination	X					
Targeted Physical Examination		X	X		X	
Obtain Rectal Temperature ^g	X	X	X		X	
30 Minutes Postvaccination Observation Period	X	X	X		X	
Adverse Experience Monitoring ^h	X	X	X	X	X	X
Assess for Serious Adverse Experiences ⁱ	X	X	X	X	X	X
Laboratory Procedures/Assessments						
Collect blood samples for immunogenicity assays (4-5 mL) ^{h, i}				X	X	X
Collect Buccal Swabs for Future Biomedical Research ^c	X					

Infant Cohort						
Visit Number:	1 ^a	2 ^a	3	4	5	6
Visit Timing:	Age:~2 months DOSE 1	Age:~4 months DOSE 2	Age:~6 months DOSE 3	30 days after Visit 3	Age:~12 to 15 months DOSE 4	30 days after Visit 5
Visit Window:	≥42 days of age to ≤90 days of age	4 months of age to 1 day prior to 5 months of age	6 months of age to 1 day prior to 7 months of age	28 to 42 days PD3	12 months of age to 1 day prior to 16 months of age	28 to 42 days PD4

a. For Visits 1 and 2, study coordinator should review the electronic Vaccination Report Card (VRC) in the vendors database at 14 days postvaccination (0 to plus 5 day window) and call the parent/legal guardian if there is a need to address questions (document phone call in study chart). The site will review VRC with parent/legal guardian at next visit.

b. Consent must be obtained prior to any study procedures.

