c. Informed consent for future biomedical research samples must be obtained before the collection of the buccal swab DNA samples. Buccal swab DNA samples for analysis should be obtained prior to the vaccination, on Day 1, on randomized subjects only, or at a later date as soon as the informed consent is obtained.

d. In order to avoid bias, the unblinded study personnel will have no further contact with study subjects for any study-related procedures/assessments following administration of the study vaccines. This includes all safety follow-up procedures. Contact between subjects and unblinded study personnel after vaccination administration is strictly prohibited.

e. Concomitant (or routine pediatric) vaccines are to be given according to recommended schedule. Any injectable concomitant vaccines provided at the visit must be given after the study vaccine and in a separate limb, may be given during the 30-minute observation period, and do not require additional observation time.

f. Adverse experiences (serious and non-serious) are to be reported from Day 1 to 14 days following each vaccination. Serious Adverse Experiences are to be reported throughout the subject's study participation.

g. Pre-vaccination temperatures taken by study staff at Visits 1, 2, 3 and 5. Parent/legal guardian to measure and record rectal temperature per VRC instructions.

h. Leftover serum samples collected from the main study will be stored for future use if the FBR consent is signed.

i. Collect blood prior to vaccination.

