7.1.2 Clinical Procedures/Assessments

7.1.2.1 Physical Examinations

For adult subjects, a targeted physical examination may be performed to assess inclusion/exclusion criteria.

For infant subjects a full physical examination will be performed at Visit 1. Any clinically significant abnormality will be recorded as part of the medical history on the appropriate eCRF. A targeted physical examination will be performed at subsequent vaccination visits (Visits 2, 3, and 5). Any clinically significant abnormality will be recorded as part of the updated medical history on the appropriate eCRF.

The full and targeted physical examination procedures both include obtaining vital signs (heart rate, respiratory rate, and oral temperature), auscultation of the heart and lung, and examination of the abdomen. In addition, a full physical examination will include an assessment of the head, eyes, ears, nose and throat (HEENT), skin, lymph nodes, neurological system, and musculoskeletal system.

Findings related to the physical examinations should be documented in the subject chart/source documentation.

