For this protocol, the broad clinical and laboratory AE categories consisting of the percentage of subjects with any AE, a vaccine related AE, a serious AE, an AE which is both vaccine-related and serious, and who discontinued due to an AE will be considered Tier 2 endpoints. For Tier 2, 95% confidence intervals will be provided for between-treatment differences in the percentage of subjects with events; these analyses will be performed using the Miettinen and Nurminen method (1985) [8], an unconditional, asymptotic method.

Table 5 Analysis Strategy for Infant Cohort Safety Parameters

Safety Tier	Safety Endpoint [†]	p-Value	95% CI for Treatment Comparison	Descriptive Statistics
Tier 1	Solicited Injection-Site and Solicited Systemic AEs	X	X	X
Tier 2	Any AE		X	X
	Any Serious AE		X	X
	Any Vaccine-Related AE		X	X
	Any Serious and Vaccine-Related AE		X	X
	Discontinuation due to AE		X	X
	Specific AEs, SOCs (incidence ≥ 4 of subjects in one of the treatment groups)		X	X
Tier 3	Specific AEs, SOCs (incidence < 4 of subjects in all of the treatment groups)			X

[†]Adverse Experience references refer to both Clinical and Laboratory AEs.
 Note: SOC=System Organ Class; X = results will be provided.

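### In infants, a non-serious adverse event starting more than 14 days after a dose need not be reported as an AE even when it stops vaccination, so the endpoint of discontinuation due to an AE may be under-counted

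*Combined protocol and SAP*

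**What the plan says.** **Reporting window.** Section 7.2 sets the duty after each later dose: "from the time of any subsequent vaccination(s) through 14 days (42 days for live attenuated vaccines) thereafter, all adverse events must be reported". Infant footnote f in Section 6.0 agrees: "Adverse experiences (serious and non-serious) are to be reported from Day 1 to 14 days following each vaccination". Serious events are treated differently: "Serious Adverse Experiences are to be reported throughout the subject's study participation".

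**Stopping.** Section 5.8 lets the investigator drop a subject for any untoward effect, without a time limit. It also allows vaccination to be stopped permanently while follow-up continues.

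**Where later findings go.** The infant flow chart has a row for Visits 2 to 6: "Update Medical History (New condition not already recorded as medical history or adverse experiences". Section 7.1.2.1 says of the targeted examinations at Visits 2, 3 and 5: "Any clinically significant abnormality will be recorded as part of the updated medical history on the appropriate eCRF".

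**The one extension.** Section 5.6 requires reporting of "Adverse events or changes to medical history occurring after the 14 days of safety follow up for Dose 3" up to discontinuation, but only for infants who meet the post-dose 3 serology rule.

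**The endpoint.** Section 8.6.2 lists the broad AE categories, ending with subjects "who discontinued due to an AE will be considered Tier 2 endpoints". Table 5 gives that row a between-group 95% CI, and Table 6 lists the same percentage for both interim analyses.

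**The concern.** The stopping rule has no time limit, but the reporting rule ends at Day 14. Take an infant with a non-serious condition that starts on Day 30 after dose 1 and is found at Visit 2, where the investigator withholds dose 2. Nothing in Section 7.2 or footnote f requires that condition to be entered as an AE, and the flow chart directs a new condition to the medical history update. Table 3 asks about intensity, relationship to vaccine and whether the vaccine was discontinued as part of evaluating an AE. The documents describe no such items for medical history.

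Safety after each dose and across all doses is the first infant primary objective, and this endpoint is one of the five broad AE categories compared with Prevnar 13. If the late stops are missing from the AE records, the Tier 2 table and the disposition table can give different numbers, and the plan has no rule to reconcile them.

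**Working it through.** The plan gives no expected rate of late, non-serious events that stop dosing, so the check has three parts: a reading of the text, a count of days, and the sensitivity of the Tier 2 interval.

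**1. Is there an exemption for events that cause discontinuation?**
- Section 7.2, before randomization: AEs are reportable if they cause exclusion from the trial. After randomization there is no matching clause for AEs that cause discontinuation.
- Section 7.1.4.1: AEs present at discontinuation are to be followed under Section 7.2, which leads back to the same window.
- Section 5.6: reporting is extended, but only for exits under the serology rule.
- The 42-day clause in Section 7.2 is for live attenuated vaccines. V114 and Prevnar 13 are conjugate vaccines, not live.

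No general exemption exists.

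**2. Share of the relevant time covered**

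The relevant period is dose 1 to dose 4, because no study dose remains to be stopped after dose 4. Inputs: doses at 2, 4, 6 and 12 to 15 months (Section 2.1), visit windows from Section 6.0, and 30.4375 days per month (a conversion assumption).

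Covered share = (3 × 14) / (days from dose 1 to dose 4).

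| Schedule | Days from dose 1 to dose 4 | Covered | Not covered |
|---|---|---|---|
| 2/4/6/12 months | 60.9 + 60.9 + 182.6 = 304.4 | 42/304.4 = 13.8% | 86.2% |
| 2/4/6/15 months | 60.9 + 60.9 + 273.9 = 395.7 | 42/395.7 = 10.6% | 89.4% |
| Shortest allowed (dose 1 at 90 days, dose 4 at 12 months) | 275.2 | 42/275.2 = 15.3% | 84.7% |
| Longest allowed (dose 1 at 42 days, dose 4 one day before 16 months) | 444.0 | 42/444.0 = 9.5% | 90.5% |

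On the nominal schedule the uncovered stretches are about 47 days before dose 2 (60.9 − 14), 47 before dose 3, and 169 to 260 before dose 4 (182.6 − 14 and 273.9 − 14).

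Sensitivity: if the 42-day clause were applied after each of doses 1 to 3 because of a concomitant live vaccine, coverage would be 126/304.4 = 41.4% to 126/395.7 = 31.8%. Between 59% and 68% of the period would still be uncovered.

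**3. How sensitive is the Tier 2 comparison?**

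One stop is 1/50 = 2 percentage points of a full arm. The Miettinen-Nurminen 95% interval is the set of differences D with |p1 − p2 − D| / √V(D) ≤ 1.96. Here V(D) = [q1(1 − q1)/n1 + q2(1 − q2)/n2] × N/(N − 1), N = n1 + n2, and q1, q2 are the maximum likelihood estimates under q1 − q2 = D. With 50 per arm:
- 3 vs 0 events: −1.4% to 16.3%. This agrees with the statement in Section 8.6.2 that the interval includes zero when both groups have fewer than 4 events.
- 4 vs 0 events: 0.5% to 18.9%.

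One unrecorded stop can therefore change whether the interval excludes zero. The counts are illustrative, not forecasts.

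**The case against.** The case against rests on five arguments.

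- **The window is deliberate.** Section 4.2.3.2 ties the 14 days to V114-003, V114-004 and other pneumococcal conjugate trials. It applies equally to all arms of a blinded, estimation-only study. This stands as a defence of 14 days for routine reporting. It does not explain why an event that ends vaccination should have no exemption.
- **Section 7.2 sets a minimum and does not forbid later entry.** This stands. A reader might infer that such an event can never reach the endpoint and that the count would be zero. The documents do not support that: the endpoint's data source is not stated, and the eCRF and data entry guidelines are not part of them.
- **Other routes exist.** Section 7.1.1.9 requires sponsor consultation and written documentation when vaccination is interrupted. Section 7.1.4.1 calls for the applicable final-visit activities when a subject leaves the trial. The flow chart marks AE monitoring at every infant visit, and Section 8.6.3 displays the primary reason for discontinuation. So the stop itself should be visible somewhere. None of these makes the late event a reportable AE or feeds it into the Table 5 row.
- **Much is already captured.** Serious events, including important medical events on medical judgment, are reported throughout. An AE that starts within 14 days and leads to a later stop is also captured. This stands and narrows the gap to late-onset non-serious events.
- **Calendar time is not event frequency.** This stands.

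A reader might also infer that the fourth pause criterion in Section 5.11 is weakened. It reads "Event which in the opinion of the investigator and/or safety monitoring committee contraindicates further dosing of additional subjects". It rests on opinion, has no 14-day limit and needs no AE record, so that inference fails.

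**Conclusion.** The concern holds as a gap in required data collection for infants between dose 1 and dose 4. As written, the plan does not oblige sites to report as an AE a non-serious event starting more than 14 days after a dose, even if it ends vaccination or participation. About 86% to 89% of the time in which a further dose could be stopped falls in that gap (about 85% to 90% at the limits of the visit windows). The Tier 2 and interim endpoint may therefore be under-counted and may disagree with the disposition table.

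The result rests on two assumptions: that sites follow the text without reporting more than it requires, and that the endpoint is built from AE records. The second is plausible but not stated. The number of missed events cannot be estimated from the documents and is probably small.

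Two wider readings should be left aside. The adult stage is barely affected, because adults receive a single dose. Nor do the documents show that every infant arm would be under-counted, since that would need at least one such event in each arm.

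**What to change.** 1. Add to Section 7.2 and infant footnote f that any AE leading to discontinuation of study vaccination or of the trial is recorded as an AE, with intensity, causality and action taken, whatever the time since vaccination.
2. State in Section 6.0 and Section 7.1.2.1 that such an event is not recorded only as updated medical history.
3. Define the Table 5 row for discontinuation due to an AE, and the matching item in Table 6, to include these events, and name the data source.

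This changes data collection only. The 14-day window for all other non-serious events and the decisions on stopping stay as they are. The cost is protocol wording, a line in the eCRF completion guideline and a few extra AE records. The reported rate of discontinuation due to an AE may be slightly higher. A matching change to the adult footnote is optional.
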